5.2 Exclusion criteria

1. History of allogeneic organ transplantation.
2. Active or prior documented autoimmune or inflammatory disorders (including inflammatory bowel disease [e.g., colitis or Crohn's disease], diverticulitis [with the exception of diverticulosis], systemic lupus erythematosus, Sarcoidosis syndrome, or Wegener syndrome [granulomatosis with polyangiitis, Graves' disease, rheumatoid arthritis, hypophysitis, uveitis, etc]). The following are exceptions to this criterion:
 - a. Patients with vitiligo or alopecia
 - b. Patients with hypothyroidism (e.g., following Hashimoto syndrome) stable on hormone replacement
 - c. Any chronic skin condition that does not require systemic therapy
 - d. Patients with celiac disease controlled by diet alone

Note: Patients without active disease in the last 5 years may be included but only after consultation with AstraZeneca.

3. History of idiopathic pulmonary fibrosis, organizing pneumonia (e.g., bronchiolitis obliterans), drug-induced pneumonitis, idiopathic pneumonitis, or evidence of active pneumonitis on screening chest CT scan
4. Uncontrolled intercurrent illness including, but not limited to, ongoing or active infection, symptomatic congestive heart failure, uncontrolled hypertension, unstable angina pectoris, cardiac arrhythmia, interstitial lung disease, serious chronic gastrointestinal conditions associated with diarrhea, or psychiatric illness/social situations that would limit

compliance with treatment requirements or compromise the ability of the patient to give written informed consent.

5. Malignancies other than SCLC within 3 years prior to screening if the patient has no evidence of disease, with the exception of those with a negligible risk of metastasis or death (e.g., expected 5-year OS > 90%) treated with expected curative outcome (such as adequately treated carcinoma in situ of the cervix, basal or squamous-cell skin cancer, localized prostate cancer treated surgically with curative intent, ductal carcinoma in situ treated surgically with curative intent).
6. History of leptomeningeal carcinomatosis.
7. History of active primary immunodeficiency.
8. Active infection including tuberculosis (clinical evaluation that includes clinical history, physical examination and radiographic findings, and tuberculosis testing in line with local practice), hepatitis B (known positive HBV surface antigen (HBsAg) result), hepatitis C, or human immunodeficiency virus (positive HIV 1 / 2 antibodies).
 - a. NOTE: Patients with a past or resolved HBV infection (defined as the presence of hepatitis B core antibody [anti-HBc] and absence of HBsAg) are eligible. Patients positive for hepatitis C (HCV) antibody are eligible only if polymerase chain reaction is negative for HCV RNA.
9. Has a paraneoplastic syndrome (PNS) of autoimmune nature, requiring systemic treatment (systemic steroids or immunosuppressive agents) or has a clinical symptomatology suggesting worsening of PNS.
10. Known allergy or hypersensitivity to Durvalumab (IMFINZI), etoposide, carboplatin, cisplatin, or any of their excipients.
11. Medical contraindication to etoposide-platinum (carboplatin or cisplatin)-based chemotherapy

Prior/concomitant therapy

12. Has received prior systemic treatment for ES-SCLC.
13. Planned consolidation chest radiation therapy.
14. Receipt of live attenuated vaccination within 30 days prior to the first dose of Durvalumab (IMFINZI). Note: Patients, if enrolled, should not receive live vaccine whilst receiving Durvalumab (IMFINZI) and up to 30 days after the last dose of Durvalumab (IMFINZI).
15. Major surgical procedure (as defined by the treating physician) within 28 days prior to the first dose of Durvalumab (IMFINZI). Note: Local surgery of isolated lesions for palliative intent is acceptable.

16. Prior exposure to any immune-mediated therapy, including, but not limited to, anti-CTLA-4, anti-PD-1, anti-PD-L1, or anti-PD-L2 antibodies, including Durvalumab/(IMFINZI).
17. Current or prior use of immunosuppressive medication within 14 days before the first dose of Durvalumab (IMFINZI). The following are exceptions to this criterion:
 - a. Intranasal, inhaled, topical steroids or local steroid injections
 - b. Systemic corticosteroids at physiological doses, which are not to exceed 10 mg/day of prednisone, or its equivalent
 - c. Systemic steroid administration required as premedication for hypersensitivity reactions (eg, CT scan premedication), or as premedication for chemotherapy is allowed.

Prior/concurrent clinical study experience

18. Participation in another clinical study with an IP during the last 4 weeks.
19. Concurrent enrollment in another clinical study, unless it is an observational (non-interventional) clinical study or during the follow-up period of an interventional study.
20. Involvement in the planning and/or conduct of the study (applies to both AstraZeneca staff and/or staff at the study site).

Other exclusions

21. Female patients who are pregnant or breast-feeding, or male or female patients of reproductive potential who are not willing to employ an effective method of birth control from screening to 90 days after the last dose of Durvalumab (IMFINZI).
22. Any condition that, in the opinion of the treating physician, would interfere with evaluation of the Program drug or interpretation of patient safety.

5.3 Lifestyle restrictions

The following restrictions apply while the patient is receiving IP and for the specified times before and after:

1. Female patient of child-bearing potential
 - Female patients of childbearing potential who are not abstinent and intend to be sexually active with a non-sterilized male partner must use at least 1 **highly** effective method of contraception (Table 4) from the time of screening throughout the total duration of the drug treatment and the drug washout period 90 days after

the last dose of durvalumab. Non-sterilized male partners of a female patient of childbearing potential must use a male condom plus spermicide throughout this period. Cessation of birth control after this point should be discussed with a responsible physician. Periodic abstinence, the rhythm method, and the withdrawal method are not acceptable methods of contraception. Female patients should refrain from breastfeeding throughout this period.

2. Male patients with a female partner of childbearing potential

- Non-sterilized male patients who are not abstinent and intend to be sexually active with a female partner of childbearing potential must use a male condom plus spermicide from the time of screening throughout the total duration of the drug treatment and the drug washout period 90 days after the last dose of durvalumab. Periodic abstinence, the rhythm method, and the withdrawal method are not acceptable methods of contraception. Male patients should refrain from sperm donation throughout this period.
- Female partners (of childbearing potential) of male patients must also use a highly effective method of contraception throughout this period (Table 4).

Please note, females of childbearing potential are defined as those who are not surgically sterile (ie, bilateral salpingectomy, bilateral oophorectomy, or complete hysterectomy) or post-menopausal.

Women will be considered post-menopausal if they have been amenorrheic for 12 months without an alternative medical cause. The following age-specific requirements apply:

- Women <50 years of age would be considered post-menopausal if they have been amenorrheic for 12 months or more following cessation of exogenous hormonal treatments and if they have luteinizing hormone and follicle-stimulating hormone levels in the post-menopausal range for the institution.
- Women \geq 50 years of age would be considered post-menopausal if they have been amenorrheic for 12 months or more following cessation of all exogenous hormonal treatments, had radiation-induced menopause with last menses >1 year ago, had chemotherapy-induced menopause with last menses >1 year ago.
- Women who are surgically sterile (ie, bilateral salpingectomy, bilateral oophorectomy, or complete hysterectomy) are eligible.

Highly effective methods of contraception, defined as one that results in a low failure rate (ie, less than 1% per year) when used consistently and correctly are described in Table 4. Note that some contraception methods are not considered highly effective (eg, male or female condom with or without spermicide; female cap, diaphragm, or sponge with or without spermicide; non-copper containing intrauterine device; progestogen-only oral hormonal contraceptive pills where inhibition of ovulation is not the primary mode of action [excluding Cerazette/desogestrel which is considered highly effective]; and triphasic combined oral contraceptive pills).

Table 4 Highly effective methods of contraception (<1% failure rate)

Barrier/intrauterine methods	Hormonal methods

 • Copper T intrauterine device • Levonorgestrel-releasing intrauterine system (eg, Mirena®)^a 	
 • Implants: Etonogestrel-releasing implants (eg, Implanon® or Norplant®) • Intravaginal Devices: Ethinylestradiol/etonogestrel-releasing intravaginal devices (eg, NuvaRing®) • Injection: Medroxyprogesterone injection (eg, Depo-Provera®) • Combined Pill: Normal and low dose combined oral contraceptive pill • Patch: Norelgestromin/ethinylestradiol-releasing transdermal system (eg, Ortho Evra®) • Minipill: Progesterone based oral contraceptive pill using desogestrel: Cerazette® is currently the only highly effective progesterone based pill

^a This is also considered a hormonal method

3. All patients: Patients should not donate blood or blood components while participating in this study and through 90 days after receipt of the final dose of durvalumab or until alternate anticancer therapy is started.
4. Restrictions relating to concomitant medications are described in Section 6.4.

5.4 Screen failures

Screen failures are patients who do not fulfill the eligibility criteria for the study, and therefore must not be included. These patients should have the reason for study withdrawal recorded as “eligibility criteria not fulfilled” (ie, patient does not meet the required inclusion/exclusion criteria). This reason for study withdrawal is only valid for screen failures (ie, not included patients). Patients may be rescreened a single time.

A minimal set of screen failure information is required to ensure transparent reporting of screen failure patients to meet the Consolidated Standards of Reporting Trials (CONSORT) publishing requirements and to respond to queries from regulatory authorities. Minimal information includes demography, screen failure details, eligibility criteria, and any serious adverse events (SAE).

6. STUDY TREATMENTS

Study treatment is defined as any investigational product(s) (including marketed product comparator and placebo) or medical device(s) intended to be administered to a study participant according to the study protocol. Study treatment in this study refers to platinum (carboplatin or cisplatin), etoposide and durvalumab.

6.1 Treatments administered

6.1.1 Investigational products

AstraZeneca will supply durvalumab (MEDI4736). SoC agents platinum (carboplatin or cisplatin) and etoposide will be supplied locally, as it is the standard treatment for these patients according usual clinical practice.

Table 5 Study treatments

	Durvalumab	Etoposide	Cisplatin	Carboplatin
Study treatment name:	Durvalumab (MEDI4736)	Etoposide	Cisplatin	Carboplatin
Dosage formulation:	500-mg vial solution for infusion after dilution, 50 mg/mL	Sourced locally by site	Sourced locally by site	Sourced locally by site
Route of administration	IV	IV	IV	IV
Dosing instructions:	Durvalumab 1500 mg via IV infusion over 60 minutes on Day 1 of each cycle.	Etoposide sequentially administered per local standards (usually over 30 to 60 minutes IV infusion) on Days 1, 2, and 3 of each cycle.	Cisplatin as an IV infusion per local standards (usually over 60 to 120 minutes on Day 1) of each cycle.	Carboplatin as an IV infusion per local standards (usually over 30 to 60 minutes on Day 1) of each cycle.
Packaging and labelling	500-mg vial solution for infusion after dilution. ^b	Sourced locally by site	Sourced locally by site	Sourced locally by site
Provider	AstraZeneca	Sourced locally by site	Sourced locally by site	Sourced locally by site

^a Label text prepared for durvalumab (MEDI4736) will show the product name as “MEDI4736” or “durvalumab (MEDI4736)” depending upon the agreed product name used in the approved study master label document. All naming conventions are correct during this transitional period. Each vial will be labelled in accordance with Good Manufacturing Practice (GMP) Annex 13 and per country regulatory requirement.

6.1.1.1 Durvalumab (MEDI4736)

Durvalumab (MEDI4736) will be supplied by AstraZeneca as a 500-mg vial solution for infusion after dilution. The solution contains 50 mg/mL durvalumab (MEDI4736), 26 mM histidine/histidine-hydrochloride, 275 mM trehalose dihydrate, and 0.02% weight/volume (w/v)

polysorbate 80; it has a pH of 6.0 and density of 1.054 g/mL. The nominal fill volume is 10.0 mL. Investigational product vials are stored at 2°C to 8°C (36°F to 46°F) and must not be frozen. Drug product should be kept in original packaging until use to prevent prolonged light exposure.

Preparation of durvalumab (MEDI4736) doses for administration with an IV bag

The dose of durvalumab (MEDI4736) for administration must be prepared by the Investigator's or site's designated IP manager using aseptic technique. Total time from needle puncture of the durvalumab (MEDI4736) vial to the start of administration should not exceed:

- 24 hours at 2°C to 8°C (36°F to 46°F)
- 4 hours at room temperature

A dose of 1500 mg (for patients >30 kg in weight) will be administered using an IV bag containing 0.9% (w/v) saline or 5% (w/v) dextrose, with a final durvalumab (MEDI4736) concentration ranging from 1 to 15 mg/mL, and delivered through an IV administration set with a 0.2- or 0.22- μ m filter. Add 30.0 mL of durvalumab (MEDI4736) (ie, 1500mg of durvalumab [MEDI4736]) to the IV bag. The IV bag size should be selected such that the final concentration is within 1 to 15 mg/mL. Mix the bag by gently inverting to ensure homogeneity of the dose in the bag.

If patient weight falls to \leq 30 kg, weight-based dosing at 20 mg/kg will be administered using an IV bag containing 0.9% (w/v) saline or 5% (w/v) dextrose, with a final durvalumab (MEDI4736) concentration ranging from 1 to 15 mg/mL, and delivered through an IV administration set with a 0.2- or 0.22- μ m filter.

Standard infusion time is one hour, however if there are interruptions during the infusion, the total allowed infusion time should not exceed 8 hours at room temperature.

Do not co-administer other drugs through the same infusion line.

The IV line will be flushed with a volume of IV diluent equal to the priming volume of the infusion set used, after the contents of the IV bag are fully administered, or complete the infusion according to institutional policy to ensure the full dose is administered.

If either preparation time or infusion time exceeds the time limits a new dose must be prepared from new vials. Durvalumab (MEDI4736) does not contain preservatives, and any unused portion must be discarded.

6.1.1.2 Etoposide + platinum

Etoposide + platinum (cisplatin or carboplatin) will be locally sourced and will be administered according to prescribing information or treatment guidance in general use by the Investigating site.

6.1.1.3 Order of Administration

Patients will receive durvalumab (1500 mg) via IV infusion over 60 minutes.

We recommend a 60-minute observation period after durvalumab is administered at least for cycle 1.

If no issues are seen after durvalumab is given during the first cycle, we recommend reducing the observation period after durvalumab administration to 30 minutes.

Durvalumab infusion will then be followed by administration following local standards of an IV infusion of carboplatin usually over 30 to 60 minutes or cisplatin usually over 60 to 120 minutes, followed by etoposide sequentially administered usually over 30 to 60 minutes infusion on Day 1 of each combination cycle; etoposide will also be administered as an IV infusion on days 2 and 3 of each cycle up until a maximum of 6 cycles has been reached.

6.1.2 Dose and treatment regimens

6.1.2.1 Durvalumab (MEDI4736)

Patients will receive 1500 mg durvalumab via IV infusion q3w in combination with EP and q4w in monotherapy until clinical progression or RECIST 1.1-defined radiological progression unless there is unacceptable toxicity, withdrawal of consent, or another discontinuation criterion is met. (Please note, if a patient's weight falls to 30 kg or below the patient should receive weight-based dosing equivalent to 20 mg/kg of durvalumab q4w after consultation between Investigator and Study Physician, until the weight improves to >30 kg, at which point the patient should start receiving the fixed dosing of durvalumab 1500 mg q4w).

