1. PROTOCOL SUMMARY

1.1 Schedule of activities (SoA)

The procedures for the screening and treatment periods in this study are presented in Table 1 and Table 2, and the procedures for the follow-up period are presented in Table 2. Patients who continue beyond Cycle 13 will continue with all Cycle 13 assessments until termination of treatment (Table 1).

Whenever vital signs and blood draws are scheduled for the same nominal time, the assessments should occur in the following order: vital signs and then blood draws. The timing of the vital signs assessments should be such that it allows the blood draw to occur at the timepoints indicated in the SoAs. Whenever electrocardiograms (ECGs), vital signs, and blood draws are scheduled for the same nominal time, the assessments should occur in the following order: ECG, vital signs, and then blood draws. The timing of the first 2 assessments should be such that it allows the blood draw to occur at the timepoints indicated in the SoAs.

For durvalumab

- Patients may delay dosing under certain circumstances.
 - Dosing may be delayed per the Dosing Modification and Toxicity Management Guidelines, due to either an immune or a non-immune-related AE.
 - If dosing must be delayed for reasons other than treatment-related toxicity, dosing will resume as soon as feasible.
 - Dosing intervals of subsequent cycles (during chemotherapy interval is 21 days, post chemotherapy interval is 28 days) may be adapted +/-3 days as clinically feasible in order to gradually align treatment cycles with the schedule of tumor efficacy (RECIST) and PRO assessments.

For EP treatment

- Patients may delay and subsequently resume dosing per local standard clinical practice.
 - If dosing must be delayed for reasons other than treatment-related toxicity, dosing will occur as soon as feasible.

Table 1 Schedule of assessments for durvalumab therapy treatment

		During Chemotherapy 1 cycle = 21 days				Post-Chemotherapy 1 cycle = 28 days				
	Screening	C1	C2	C3	C4-C6	C5-C7 to PD		End of treatment		
Week	-4 to -1	0	Q3w ±3 days during chemotherapy and q4w ±3 days post-chemotherapy, unless dosing needs to be held for toxicity reasons							
Day	-28 to -1	1 ^a	Q21days ±3 days during chemotherapy and q28days ±3 days post-chemotherapy, unless dosing needs to be held for toxicity reasons							For details, see Section
Informed Consent										
Informed consent: study procedures ^b	X								5.1	

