A convenience sample size of approximately 85 patients was estimated based on the expected accrual potential during 6 months in 30 sites, although the recruitment duration may be reduced or extended, until P&R approval of durvalumab in Spain for ES-SCLC based on CASPIAN results, and the number of patients recruited could be higher. A maximum of 30% of recruited patients will have ECOG performance status of 2 at baseline.

Treatments and treatment duration:

Durvalumab will be concurrently administered with first-line chemotherapy (EP) on an every 3 week (q3w) schedule for 4 to 6 cycles, and will continue to be administered post-chemotherapy on an every 4 week (q4w) schedule until confirmed progressive disease (PD) or unacceptable toxicity.

Durvalumab + chemotherapy combination

- Durvalumab 1500 mg via IV infusion q3w concurrently with chemotherapy, starting on Week 0, for 4-6 cycles. Please note, if a patient's weight falls to 30 kg or below (≤ 30 kg), then the patient should receive weight-based dosing equivalent to 20 mg/kg of durvalumab after consultation between the Investigator and Study Physician, until the weight improves to above 30 kg (>30 kg), at which point the patient should start receiving the fixed dosing of durvalumab 1500 mg.
- EP: the dose of etoposide + carboplatin or cisplatin investigated will not exceed the product label dose for the given indication dose (etoposide [80 to 100 mg/m²] via IV infusion with either carboplatin [area under the curve (AUC) 5-6] via IV infusion or cisplatin [75 to 80 mg/m²] via IV infusion), starting on Week 0, for 4-6 cycles.

Durvalumab monotherapy

- Durvalumab 1500 mg via IV infusion q4w, starting 3 weeks after the last infusion of the combination, until confirmed progressive disease (PD) or unacceptable toxicity. Please note, if a patient's weight falls to 30 kg or below (≤ 30 kg), then the patient should receive weight-based dosing equivalent to 20 mg/kg of durvalumab q4w after consultation between Investigator and Study Physician, until the weight improves to above 30 kg (>30 kg), at which point the patient should start receiving the fixed dosing of durvalumab 1500 mg q4w.

Duration of treatment

Unless specific treatment discontinuation criteria are met, patients will continue therapy until clinical progression or confirmed radiological progression (defined in Appendix E).

Progression during treatment

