6.1.2.2 Etoposide + platinum

Patients will receive, according to SoC, 4-6 cycles of:

- Etoposide: 80 to 100 mg/m² daily on Days 1 to 3 (total dose 300 mg/m²) given q3w plus
- Carboplatin: AUC 5-6 on Day 1 given q3w, or
- Cisplatin: 75 to 80 mg/m² intravenous (IV) on Day 1 given q3w

Cisplatin and carboplatin have indistinguishable clinical efficacy but are different in terms of cost and toxicity profiles. The selection of cisplatin or carboplatin in combination with etoposide is at the investigator's discretion. These agents are commonly used in ES-SCLC and will be given as per the product label for the indication and the NCCN and ESMO guidelines.

Prophylactic cranial irradiation (PCI) will be permitted; this will be at the investigators' discretion as per SoC guidance for ES-SCLC.

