Appendix A Regulatory, ethical and study oversight considerations

A 1 Regulatory and ethical considerations

This study will be conducted in accordance with the protocol and with the following:

- Consensus ethical principles derived from international guidelines including the Declaration of Helsinki and Council for International Organizations of Medical Sciences (CIOMS) International Ethical Guidelines
- Applicable ICH Good Clinical Practice (GCP) Guidelines
- Applicable laws and regulations
- AstraZeneca will be responsible for obtaining the required authorisations to conduct the study from the concerned Regulatory Authority. This responsibility may be delegated to a CRO but the accountability remains with AstraZeneca.

The protocol, protocol amendments, ICF, Investigator Brochure, and other relevant documents (eg, advertisements) must be submitted to an IRB/IEC by the sponsor and reviewed and approved by the IRB/IEC before the study is initiated.

Any amendments to the protocol will require IRB/IEC approval before implementation of changes made to the study design, except for changes necessary to eliminate an immediate hazard to study patients.

Regulatory Reporting Requirements for SAEs

Prompt notification by the investigator to the sponsor of a SAE is essential so that legal obligations and ethical responsibilities towards the safety of participants and the safety of a study intervention under clinical investigation are met.

The sponsor has a legal responsibility to notify both the local regulatory authority and other regulatory agencies about the safety of a study intervention under clinical investigation. The sponsor will comply with country-specific regulatory requirements relating to safety reporting to the regulatory authority, Institutional Review Boards (IRB)/Independent Ethics Committees (IEC), and investigators.

For all studies except those utilizing medical devices investigator safety reports must be prepared for suspected unexpected serious adverse reactions (SUSAR) according to local regulatory requirements and sponsor policy and forwarded to investigators as necessary.

An investigator who receives an investigator safety report describing a SAE or other specific safety information (eg, summary or listing of SAEs) from the sponsor will review and then file it along with the [Investigator's Brochure or state other documents] and will notify the IRB/IEC, if appropriate according to local requirements.

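### Protocol 6.1.2 misstates two doses: the low-weight durvalumab note gives only the q4w interval although q3w cycles are also covered, and the etoposide total of 300 mg/m² fits only the top of its range

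*Protocol*

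**What the plan says.** **Durvalumab.** Protocol 6.1.2.1 sets "1500 mg durvalumab via IV infusion q3w in combination with EP and q4w in monotherapy". A note in parentheses then deals with patients whose weight falls to 30 kg or below. It prescribes "weight-based dosing equivalent to 20 mg/kg of durvalumab q4w after consultation between Investigator and Study Physician" and, once weight recovers, a return to 1500 mg, again q4w. The note is not confined to one treatment phase.

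Elsewhere the documents treat the interval as follows:

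- The synopsis (1.2) and SAP 4.1.2 carry two low-weight notes, one per phase. The note under the q3w combination regimen reads "weight-based dosing equivalent to 20 mg/kg of durvalumab after consultation between the Investigator and Study Physician", with no q4w. Only the monotherapy note says q4w.
- Protocol 6.1.1.1 says "weight-based dosing at 20 mg/kg will be administered using an IV bag" and gives no interval.
- The schedule of activities (1.1) states the intervals as "during chemotherapy interval is 21 days, post chemotherapy interval is 28 days", each adaptable by 3 days either way.
- Table 5 (6.1.1) gives "Durvalumab 1500 mg via IV infusion over 60 minutes on Day 1 of each cycle".

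**Etoposide.** Protocol 6.1.2.2 gives "80 to 100 mg/m² daily on Days 1 to 3 (total dose 300 mg/m²" as the dose per 3-week cycle. The synopsis and SAP 4.1.2 give the same daily range and state no total.

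**The concern.** Section 4.1 sends the reader to Section 6.1 for treatment details, so 6.1.2 should be correct on its own. It contains two separate slips.

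First, a site that follows the low-weight note literally during chemotherapy would move the patient from a 21-day to a 28-day durvalumab interval. Durvalumab would then no longer fall on Day 1 with etoposide and platinum, and the patient would receive less drug per week. No section gives a reason for a longer interval at low weight.

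Second, the single etoposide total is wrong for every permitted daily dose below 100 mg/m².

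The specified dose also serves as a safety reference: sections 8.4.3.1 and 8.4.3.2 define overdose against the dose in the protocol. It should therefore have one clear value or range.

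**Working it through.** **1. Low-weight durvalumab interval**

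Inputs: 20 mg/kg (6.1.2.1); a 30 kg patient, the weight used in the Appendix F example; q3w with chemotherapy and q4w afterwards (6.1.2.1, synopsis, SAP 4.1.2); windows of ±3 days (1.1).

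- Dose: 20 mg/kg × 30 kg = 600 mg, as in Appendix F.
- Weekly dose at q3w: 600 / 3 = 200 mg/week.
- Weekly dose at q4w: 600 / 4 = 150 mg/week.
- Shortfall if the note is followed during chemotherapy: 1 − 150/200 = 25%.
- The return to 1500 mg q4w has the same shortfall while chemotherapy continues: 1500/4 = 375 against 1500/3 = 500 mg/week, again 25%.

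Could the scheduling window absorb the difference?

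- During chemotherapy: 21 ± 3 = 18 to 24 days.
- After chemotherapy: 28 ± 3 = 25 to 31 days.
- The windows do not overlap. A 28-day interval is 28 − 24 = 4 days past the longest allowed during chemotherapy.

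Example: low weight is found at cycle 2 (week 3), with no other delays.

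| Infusion | Chemotherapy (q3w) | Durvalumab under the note (q4w) | Gap |
|---|---|---|---|
| 1 | week 3 | week 3 | 0 weeks |
| 2 | week 6 | week 7 | 1 week |
| 3 | week 9 | week 11 | 2 weeks |

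**2. Etoposide total per cycle**

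Inputs: 80 to 100 mg/m² daily on Days 1 to 3 (6.1.2.2; Table 5 also gives three days). Total = daily dose × 3.

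| Daily dose (mg/m²) | Total per cycle (mg/m²) | Equals the stated 300? |
|---|---|---|
| 80 | 3 × 80 = 240 | no |
| 90 | 3 × 90 = 270 | no |
| 100 | 3 × 100 = 300 | yes |

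The plan's figure is reproduced only at 100 mg/m². At 80 mg/m² it overstates the total by 300 − 240 = 60 mg/m², which is 60/240 = 25%.

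**The case against.** The case for leaving the text alone has four parts.

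- **The correct interval is stated elsewhere.** The opening sentence of 6.1.2.1, the schedule of activities and Table 5 all point to q3w with chemotherapy, and the synopsis has a combination note without q4w. The phrase in 6.1.2.1 matches the synopsis's monotherapy note word for word, so it looks like an omission rather than a competing regimen. That reading is probably right, but it supports the correction: it explains how the error arose and leaves the text wrong.
- **There is a safeguard and almost no exposure.** The switch requires consultation with the Study Physician, and a patient must enter above 30 kg and fall to 30 kg or below within 4 to 6 cycles. This stands and limits the risk. The 25% describes a literal reading in a rare patient and is not an expected effect in the trial.
- **300 mg/m² may be meant as a ceiling.** The synopsis caps chemotherapy at the product label dose, so this is a reasonable guess at the intent. But 6.1.2.2 does not present the figure as a maximum.
- **Nothing depends on the etoposide total.** Sites dose from the daily range, chemotherapy follows prescribing information and local practice, and SAP 4.3.4.1 specifies a programmed dose only for cisplatin and carboplatin. This also stands, and it is why the point is minor.

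**Conclusion.** Both statements are wrong as written, and the point is minor. The low-weight note gives the wrong interval for combination cycles. At 30 kg, a literal reading lowers the weekly durvalumab dose by 25% and sets an interval 4 days outside the permitted window. The etoposide total should be a range, 240 to 300 mg/m² per cycle; the stated 300 is right only at 100 mg/m² daily.

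The first conclusion assumes that the two-note form in the synopsis and SAP reflects the intended regimen, which the schedule of activities and Table 5 support. The 25% applies only if the note is followed literally and not corrected at consultation. Few or no patients are expected to be affected. The second conclusion is arithmetic within 6.1.2.2 and involves no conflict with the synopsis or SAP. Neither slip touches the endpoints, the precision of the estimates or the analysis.

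**What to change.** - **6.1.2.1:** state that a patient at 30 kg or below receives 20 mg/kg q3w while on chemotherapy and q4w in monotherapy, still after consultation with the Study Physician, and returns to 1500 mg at the interval of the current phase once weight exceeds 30 kg.
- **6.1.2.2:** replace the single etoposide total with 240 to 300 mg/m² per cycle.

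The cost is two wording corrections. They can go into the next protocol amendment, since Appendix A 1 says "Any amendments to the protocol will require IRB/IEC approval before implementation of changes made to the study design". The SAP, the analysis and recruitment need no change.
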